- 2 * Discuss the research design including but not limited to such issues as: probability of group assignment, potential for subject to be randomized to placebo group, use of control subjects, etc.:

Volunteers with a DSM-IV diagnosis of schizophrenia or schizoaffective disorder will be recruited, screened, and allocated in a double-blind manner to either the Nicotine Group or the Placebo Group. All participants will be asked to perform 10 weeks of cognitive remediation training (Posit Science, Duncan, SC), with daily training sessions Monday through Friday. On Mondays and Thursdays, all participants receive a lozenge 20 min prior to the training. In the Nicotine Group, the lozenge will contain 2 or 4 mg of nicotine, depending on smoking status. In the Placebo Group, the lozenge will be a matched placebo.

Outcome measures (OCMs) are assessed on Wednesdays in week 0 (day before training starts), weeks 4, 7 and 10 (after the training session), and week 14 (four weeks after training ends). OCMs are assessed on a non-drug day (Wed) because we are not studying the acute effects of nicotine but nicotine-induced enhancement of longer-term training effects.

- 3 * Describe the relevant prior experience and gaps in current knowledge. Describe any relevant preliminary data:

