
remind them to take the lozenge 20 min before the training. The participant would be allowed to keep up to two lozenges at home, for the event that they meet unexpected obstacles to coming to the MPRC on a lozenge day. Their performance would be monitored and recorded via an internet portal maintained by Posit Science Inc. Participants may take breaks but are encouraged to first complete the current exercise. We allow some flexibility in the above training and testing schedule because it will be unavoidable that some participants will be unavailable on some days. In general, if one lozenge session is missed, the lozenge will be given on the following day. If an outcome measurement day is missed, outcome measurements will be performed on either Tuesday or Friday of the same week (thus avoiding lozenge days), or if not feasible, in the preceding or following week. If an entire week of training is omitted by an otherwise reliable participant, the following weeks of the schedule will be moved back by one week.

- 2 * Describe all procedures already being performed for diagnostic or treatment purposes (if not applicable to the study, enter "N/A"):

N/A

- 3 * Describe the duration of an individual participant's participation in the study:

The cognitive training intervention will take 10 weeks. A follow-up outcome assessment session will be scheduled 4 weeks following training completion, but we will allow up to 10 weeks before a participant is labeled as "lost to follow-up". We will allow up to 3 months between consent and the next study session; after this, a participant would have to be re-consented. We will allow up to 3 months between the last nicotine exposure session and the beginning of the cognitive training. Thus, the maximum duration of participation is 12 months. If more than 3 months elapsed between the screening and the beginning of the training procedure, we would repeat most of the screening procedures prior to the start. A study physician would determine which procedure need to be repeated.

- 4 * Describe the duration of the entire study:

We anticipate that data collection will be completed in two years. Data analyses and preparation for publication may continue thereafter.

- 5 * Describe any additional participant requirements:

None.

ID: VIEW4E0280585B400

Name: v2_Study Procedures

View: v2_Sample Size and Data Analysis

Sample Size and Data Analysis

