If you uploaded a separate research protocol document in the 'Research Protocol' page, cite the applicable section and page numbers from that document in the answer boxes below.

- 1 * Provide the rationale and sample size calculations for the proposed target population:

Statistical and power analyses: Hypothesis 1a (larger or faster improvement in Nicotine than Placebo Group): Assuming training effects are linear with time, we will conduct an intention to treat (ITT) analysis by fitting the mixed model regression for repeated measures OCM= time+ treatment+ treatment x time, with time as a continuous measure. The treatment x time interaction estimates the difference between treatment groups in OCM rate of change (slope). Although we will include subjects with partial data, the effect size detectable was estimated conservatively⁷⁸ by: $d = [2(z_a + z_b)2(1-r)/bnVar(t)]/2$, where d = (difference in slopes)/SD(OCM), r = within-subject correlation of OCM, $b=4$ visits per subject, n = number of completers per group, $Var(t)=0.185$ is the within-subject variance of the visit times, and $z_a=1.96$ and $z_b=0.84$ for two-sided $\alpha=0.05$ and power=0.80. With $n=20$ completers per group, $d=0.56$ (a medium effect size) will be detectable for $r=0.7$ consistent with the high ICC of the MCCB, the primary OCM. To explore differences in treatment effects between MCCB domains, we will employ the mixed model for repeated measures: T-score= domain+ treatment+ time+ interactions. In particular, the domain x treatment x time interaction assesses variation among domains in the magnitude of the treatment effects on change slopes in OCM scores. In secondary analyses to guide the design of future studies, we will fit a model in which time is treated as a categorical measure unconstrained by a linear fit to explore different learning scenarios such as a more rapid initial acquisition but similar ceiling. In this model, we will add week 14 data to examine Hypothesis 1b (persistence of improvements after training ends), comparing treatment groups on the difference between week 14 and 10. Other exploratory analyses: 1) Smoking status (smoker, never-smoker) is added as an exploratory between-subject factor. 2) A further regression will explore differences between treatment groups in two compliance measures, the cumulative percentage of missed training sessions and lozenge administrations until each OCM time point. If treatment groups differ on compliance, we would include time-dependent compliance as a mediator of treatment effects. A descriptive analysis to support Hypothesis 1a will compare the percentage of participants in each group that achieves clinically significant improvement in MCCB composite scores (6 points from baseline adjusted for practice effects, see above) at each OCM time point.

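### The make-up rule does not exempt the week-10 battery, and follow-up is accepted up to 10 weeks after training, while the persistence analysis has one week-14 level and no stated window

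*Combined protocol and SAP*

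**What the plan says.** **Planned timing.** Justification, Objective, & Research Design, item 2, puts the assessments on Wednesdays: week 0, then "weeks 4, 7 and 10 (after the training session), and week 14 (four weeks after training ends".

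**General make-up rule.** Study Procedures, item 1: "If an outcome measurement day is missed, outcome measurements will be performed on either Tuesday or Friday of the same week", "or if not feasible, in the preceding or following week". The rule covers every outcome day. If a whole training week is omitted by a reliable participant, "the following weeks of the schedule will be moved back by one week", so the schedule shifts as a block.

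**Follow-up rule.** Study Procedures, item 3: "The cognitive training intervention will take 10 weeks". Then: "A follow-up outcome assessment session will be scheduled 4 weeks following training completion, but we will allow up to 10 weeks", after which the participant is labelled lost to follow-up.

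**What week 10 is meant to measure.** Four places define measures at this visit as post-training:
- Study Procedures, item 1, lists a set taken only before and after training (working-memory capacity, UCSD skills assessment, Quality of Life Scale, trait anxiety, Cognitive Assessment Interview, treatment guess, blood sample).
- Surveys/Questionnaires, item 1, ties the treatment guess to the assessment directly after training is completed.
- Testing, item 2, places the change localization task directly before and directly after training.
- Sample Collection/Analysis, item 4, takes blood before and after the intervention.

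**Analysis.** Sample Size and Data Analysis, item 1, examines Hypothesis 1b within secondary analyses. It adds week-14 data to a categorical-time model, "comparing treatment groups on the difference between week 14 and 10". No analysis window, actual-time term or sensitivity analysis for early or late visits is given.

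**The concern.** Persistence is a function of time since training stopped. A contrast labelled week 14 minus week 10 reads as a 4-week effect, but the visit rules admit other intervals under the same label, and nothing in the analysis plan separates them. If late visits go into the week-14 level, the estimate averages over an unplanned mix of intervals and loses precision. If one arm happened to return later, the arm comparison would also be partly a comparison of time since training.

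The week-10 rule raises a separate problem. A battery taken in week 9 is not a post-training measurement, yet it would supply the post-training value for the measures taken only twice and the starting point of the persistence contrast.

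**Working it through.** **1. Reproduce the plan's calendar.** Inputs: baseline on Wednesday of week 0, training from the next day, five sessions a week for 10 weeks, lozenges on Mondays and Thursdays.
- Sessions from Thursday of week 0 to Wednesday of week 10: 2 + 9 × 5 + 3 = 50.
- Lozenge days: 1 + 9 × 2 + 1 = 20, which matches the 20 lozenge sessions in Sample Size and Data Analysis, item 1.
- Wednesday of week 10 is therefore the last training day, and the planned interval is 14 − 10 = 4 weeks, as stated.

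**2. Apply the make-up rule to week 10.**
- Wednesday of week 9: sessions done = 2 + 8 × 5 + 3 = 45 of 50; lozenges = 1 + 8 × 2 + 1 = 18 of 20. Five sessions and two lozenges remain.
- The same-week Tuesday option also falls one day before the last session (49 of 50 done).

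**3. Apply the follow-up rule.** I read the 10 weeks as counted from training completion, so the latest visit is 10 + 10 = week 20. (Counting from the scheduled visit would give 14 + 10 = week 24. The stated 12-month maximum participation fits either reading and does not settle it.)

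| Case | Interval between the two assessments |
|---|---|
| Planned | 14 − 10 = 4 weeks |
| Week 10 on time, follow-up rule only | 14 − 10 = 4 to 20 − 10 = 10 weeks |
| Week 10 on time, one-week rule also applied to follow-up | 13 − 10 = 3 to 20 − 10 = 10 weeks |
| Both visits at opposite limits | 13 − 11 = 2 to 20 − 9 = 11 weeks |

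**4. What the mix could mean (illustration on assumed values).** The documents give no decay rate for a nicotine-related gain. If a between-arm difference decays exponentially, the share left after t weeks with half-life h is 0.5^(t/h).

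| Assumed half-life | Left at 4 weeks | Left at 10 weeks |
|---|---|---|
| 4 weeks | 50% | 18% |
| 8 weeks | 71% | 42% |
| 16 weeks | 84% | 65% |
| No decay | 100% | 100% |

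The effect of mixing intervals therefore ranges from none to large, depending on a rate the trial does not know.

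**5. What an early week-10 battery costs.** If the training effect is linear in sessions, 45/50 = 90% of it has accrued by Wednesday of week 9, a 10% understatement for that participant. If, as an assumption, one participant in ten were affected, the average understatement would be 0.10 × 10% = 1%.

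**The case against.** **The specific text should govern.** The make-up rule is a general fallback, used only when other days of the same week are not feasible, and an assessment can be moved to an earlier week only when the absence is foreseen. The four passages that define post-training measures are more specific. This makes a week-9 battery an unlikely intention, but it does not remove the conflict: the rule is stated without exception, and staff scheduling a visit would apply it as written.

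**The 10-week limit concerns retention.** It says when someone is labelled lost, not how a late visit is analysed. A reader might infer that a week-20 visit is coded as week 14. The plan never says so; that is drawn from its having no other level for such a visit. What stands is that the handling is unstated.

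**The extremes are not typical.** A reader might take 2 to 11 weeks as the working range. Those figures need the two visits at opposite limits, and the 11 also needs the disputed week-9 battery. Nothing in the documents suggests how often that would happen.

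**Slow decay is plausible.** The background in Justification, Objective, & Research Design, item 4, reports that effects of this training approach lasted to 6 months. At 26 weeks the assumed half-lives would leave only about 1%, 11% and 32%. That evidence concerns training rather than the added effect of nicotine, but it is a fair reason not to lean on the decay table.

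**Consequences are limited.** The windows are the same in both arms and allocation is double-blind. A generous follow-up window also protects retention when about 20 completers per group are expected. All of this stands, and it keeps the point modest.

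**Conclusion.** The point holds in a limited form. The make-up rule, as written, allows a post-training battery before training ends and must be reconciled with the passages that define it as post-training. The follow-up rule allows an interval of 4 to 10 weeks where 4 is planned (3 to 10 if the one-week rule applies too), and the persistence analysis does not say how such visits are handled. This assumes that the 10 weeks run from training completion and that week 10 is on time.

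The main consequence is a blurred 4-week estimand and extra variance in a secondary analysis.

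Two stronger conclusions are not supported. A reader might infer that the arm comparison is biased. That requires visit timing to differ by arm, and the documents give no mechanism for it, although chance imbalance is possible in groups of this size and the plan has no step that would show it. A reader might also infer that the primary result is at risk. The primary slope model does not use week 14, and an occasional week-9 battery would shift its last point only slightly.

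**What to change.** 1. **Week-10 make-up.** In Study Procedures, item 1, state that a missed week-10 battery is done only after the last training session, in the same or the following week. Align this with the list of post-training measures in the same item, Surveys/Questionnaires item 1, Testing item 2 and Sample Collection/Analysis item 4.
2. **Main Hypothesis 1b analysis.** State that all follow-up visits up to the 10-week limit are kept, and say from which date that limit is counted.
3. **Reporting.** Tabulate actual weeks since the last training session at follow-up, by arm.
4. **Sensitivity analysis.** Repeat the Hypothesis 1b contrast using only follow-ups within one week of the planned 4 weeks (weeks 13 to 15).
5. **Optional, exploratory.** Fit a model with actual weeks since training and its interaction with treatment. With about 20 completers per group this will be imprecise, so it should not be the main estimate.

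**Cost.** This is mainly a change of wording. Interviews item 4 and Observation item 3 already put dates on the rating forms and score sheets, so visit timing should be recoverable without new data collection. Scheduling at week 10 becomes slightly less free, and a participant known to be away in weeks 10 and 11 could lose the last training-phase observation. The sensitivity analysis is smaller and conditions on return time, which arises after randomisation and may be related to clinical state, so it is supportive only.

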Volunteers who provide Informed Consent will be screened for all Inclusion/Exclusion criteria. SCREENING will include: - Verification of age. - The SCID, to determine the presence/absence of current psychiatric conditions. For most patients, a SCID will have already been obtained and does not need to be repeated. - Medical history targeted at the cardiovascular, neurological, cognitive and other exclusion criteria. - Blood pressure and heart-rate reading. - ECG (12-lead with 3-5 minute rhythm strip). Exclusionary conditions documented on ECG include: Wolfe Parkinson White syndrome Myocardial ischemia and infarction Complete left bundle branch block PR interval <120 ms or >200 ms Prolonged QT interval (corrected) >500 ms Cardiac arrhythmias as defined by PACs >3 per min or PVCs >1 per min - Urine drug test, as a possible indication for substance abuse or dependence (may be repeated at any time during the study if intoxication is suspected) - Alcohol breathalyzer test, as a possible indication for alcohol abuse or dependence (may be repeated at any time during the study if intoxication is suspected) - Urine pregnancy test for females (also performed at the beginning of the cognitive training phase, and every two weeks thereafter) - Targeted questions about smoking history and motivation to stop smoking - Breath CO reading, as an indicator of smoking status and frequency - Listing of all currently taken medication - Vision test - The Addiction Severity Index - Drug and Alcohol Use subscale as an indicator for substance abuse or dependence. - The Wechsler Abbreviated Scale of Intelligence (WASI), as an indicator for possible mental retardation. Volunteers who pass the screening will be randomized to either the nicotine group or the placebo group. Randomization will be performed by the MPRC's biostatistician, [name], upon receiving a randomization request from the research assistant coordinating the study or a study investigator. Participants are then scheduled for a first NICOTINE EXPOSURE SESSION. In this session, participants will consume a nicotine lozenge (2 mg for non-smokers, 4 mg for smokers) if they have been randomized to the nicotine group and a placebo lozenge if they have been randomized to the placebo group. The number of smokers will be counterbalanced between the nicotine and placebo group. Participants will be instructed not to eat or drink within 15 min prior to or while consuming the lozenge. Participants are asked to report any adverse effects as soon as noted and to rate their subjective state immediately before the lozenge and every 30 min thereafter (see Side-Effects Checklist under "Additional Documents"). At this time, an investigator will also take their blood pressure and heart rate. The adverse effects of nicotine develop rapid tolerance. If any adverse effects are observed that are greater than "mild" and were not present pre-lozenge, the participant will undergo another lozenge exposure session on a separate day before starting the study. This may be repeated up to 4 times. Once both the participant and the investigator judge that any untoward effects of the lozenge are mild and tolerable and will not interfere with the cognitive training, the first outcome measurement session is scheduled, and the daily training sessions will commence the day after. A smoker who cannot tolerate the 4-mg lozenge may be dosed with a 2-mg lozenge in the cognitive training phase (the study would be single-blind for this subject). A participant who cannot tolerate the 2-mg lozenge even after repeated attempts will be excluded from the study. Participants who with the 2 mg lozenge display a rise in blood pressure by >20 mm Hg relative to pre-lozenge, a rise in HR to >120, or vomiting, will also be excluded from the study. OUTCOME MEASUREMENTS will be performed before the training begins, and approximately every 4 weeks after that until 4 weeks after the training ends. During the training phase, the outcome measurements will be performed AFTER completion of the daily cognitive training session. We will always schedule at least 1 hour between training and the outcome measurement, during which the participant can rest or have lunch. Outcome assessments are: a) The MATRICS Consensus Cognitive Battery (MCCB), an FDA-approved assessment tool for trials of cognition-enhancing treatments in PSZ. The battery measures 7 domains: speed of processing, attention/vigilance, working memory (verbal, nonverbal), verbal learning, reasoning, problem solving, and social cognition. b) The progression in training exercise parameters since the last outcome measurement time point (see below). c) Symptom assessments: the Brief Psychiatric Rating Scale, Scale for Assessment of Negative Symptoms, and Calgary Depression Scale. d) The state version of the State-Trait Anxiety Inventory. e) The Cogstate computerized assessment battery. Further outcome measures taken only pre- and post-training (week 0 and 10): a) Working Memory capacity (K) derived from a computerized change localization task. Two to four colored squares are shown for 100 ms. After a delay, they reappear and the task is to click on the one square that has changed color. b) The UCSD Performance-Based Skills Assessment, measuring ability to perform real-life tasks by standardized role-play. c) Quality of Life Scale, measuring functional outcome and quality of life in PSZ. d) The trait version of the State-Trait Anxiety Inventory. e) The Cognitive Assessment Interview (CAI), a brief interview-based measure of daily life cognitive functioning, administered to both the PSZ and a close relative or caretaker. The CAI was developed based on two longer scales and assesses 10 items related to working memory, attention/vigilance, learning/memory, problem solving, processing speed, and social cognition, with little or no repetition effects. f) Questionnaire asking each participant to guess their treatment group (nicotine or placebo; post-training only). g) A 5-ml venous blood sample will be taken, centrifuged, and frozen. At the completion of the study, the samples will be analyzed for TNF alpha, and potentially other inflammatory markers, to test whether repeated nicotine exposure may have anti-inflammatory effects that may be related to any effects on cognitive outcome measures. If a participant declines to have their blood drawn but are otherwise eligible for the study, they may participate without the blood draws. COGNITIVE REMEDIATION TRAINING PROCEDURE Prior to each daily training session, participants will complete a brief checklist about their caffeine and cigarette consumption today (how much/how many), when they last smoked/drank a caffeinated beverage, how many hours of sleep they got the previous night, when they last drank alcohol and how much. Prior to each session, smokers also provide a CO breathalyzer reading. Each training session will include ~30 min of auditory and ~30 min of visual training exercises by Posit Science, in a counterbalanced manner. The auditory training consists of six exercises: fast and accurate discrimination of (1) sound frequencies, (2) phonemes and (3) syllables, and recall of syllables, (4) sequences of syllables, (5) multi-element verbal instructions, and (6) details of a narrative. The visual training consists of five exercises designed to (1) improve visual precision, (2) increase capacity to divide visual attention, (3) improve visual memory, (4) expand field of view, and (5) increase visual processing speed. The programs train the fine-tuned and differentiated processing of sensory input and engage attention, working memory and/or executive processes. To induce the right level of challenge and promote engagement and motivation, task difficulty adjusts continuously to user performance to maintain ~85% correct responses (which are rewarded by auditory and visual feedback). Adjustable parameters include presentation time, interstimulus interval, physical similarity between stimuli, stimulus eccentricity, number of stimuli, and information complexity. Some exercises provide a progress summary of these parameters after each session. These values will be recorded on all training days. Other exercises provide a separate assessment tool to monitor progress. These assessments will be performed every 4 weeks with other outcome measurements. Every Monday and Thursday, a nicotine or placebo lozenge, encapsulated in gelatin, will be administered 20 minutes prior to the beginning of the training. Nicotine lozenges are mint-flavored "mini" lozenges, placebo lozenges are size-matched breath mints. Smokers in the Nicotine Group will receive a 4-mg lozenge. Plasma concentrations after this dose resemble the "nicotine boost" typically seen in dependent smokers by smoking a single cigarette (~1 ng/ml). Non-smokers in the Nicotine Group will receive a 2-mg lozenge because 4 mg in nicotine-naïve individuals would likely result in low tolerability. Participants will be instructed not to eat or drink within 15 min prior to or while consuming their lozenge. Participants may perform the training sessions at the Maryland Psychiatric Research Center (MPRC), or, in a separate room, at their day program or inpatient unit if applicable (a research associate would visit daily with laptop, lozenge or assessment instruments). The lozenge would be administered by a local nurse or other medical professional if possible, else these sessions would be performed at the MPRC. Participants who are unable to come to the MPRC or day program to complete the training (e.g., because they work or live too far away) may perform the exercises at home if they have internet access and their clinician or study staff considers them capable of doing so reliably. The CO measurement would be omitted on home-training days, and participants would be given the questionnaire about how much they slept and how much caffeine or alcohol they consumed to complete by themselves at home. On the two weekly lozenge days, they would be scheduled to perform the training at the MPRC. Under select circumstances, when the patient is unable to come to the MPRC on those days, too, they would be instructed to take the lozenge at home, following doctor's orders. A study team member would call them at home and

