
Hypothesis 2a (training progress within nicotine vs. placebo sessions): For those adaptive exercise parameters for which progress is stated at the end of each session, we will compare nicotine - placebo differences on within-session progress, averaged over 20 lozenge-sessions, between treatment groups using a t-test. Power is estimated from the formula⁷⁸ $d = [2(z_a + z_b)2(1-(b-1)r)/bn]$, where d = (difference in average change)/SD(change within 1 session), $b=20$ visits per subject, and other terms are defined as above. For $n=20$ completers per group, we would have power=0.80 at two-sided $\alpha=0.05$ to detect $d=0.51$ (a medium effect size) for $r=0.3$. r is estimated based on each exercise being short and of potentially low reliability. To test Hypothesis 2b (persistence of nicotine-induced improvements beyond the presence of nicotine), we will analyze within-session progress on no-lozenge sessions. If progress made in the nicotine sessions does not persist, we would expect a performance decrement in subsequent no-lozenge sessions (Tue, Fri), whose difficulty levels begin where the previous session left off. If progress made under nicotine does persist, we would expect no decrement and progress comparable to no-lozenge sessions in the placebo group.

To achieve 20 completers per group, we expect having to enroll 25 subjects per group into the training and having to screen approximately 70 subjects in total.

Please note that screening is part of the study protocol. Thus, we expect to consent 70 subjects.

- 2 * Provide the plan for data analysis. Include in the description the types of comparisons that are planned (e.g., comparison of means, comparison of proportions, regressions, analysis of variance, etc.), which is the primary comparison/analysis, and how the analyses proposed will relate to the primary purposes of the study:

Please see above. The sample size calculation is closely related to the planned analyses.

ID: VIEW4E02806052800

Name: v2_Sample Size and Data Analysis

View: v2_Sharing of Results

Sharing of Results

- 1 * Describe whether results (study results or individual subject results, such as results of investigational diagnostic tests, genetic tests, or incidental findings) will be shared with subjects or others (e.g., the subject's primary care physicians) and if so, describe how it will be shared:

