All effects are temporary and will dissipate spontaneously with the metabolism of nicotine (half-life: 2.3 hours for the lozenge). Only individuals who meet certain medical history criteria will be admitted into the study. Participants will consume at least one lozenge before the training program starts. Subjective and cardiovascular (blood pressure, heart rate) effects of the lozenge will be monitored for 3 hours. This will identify subjects prone to experiencing any greater than expected untoward effects, such as a rise in blood pressure by >20 mm Hg, a rise in HR to >120, or vomiting. Such subjects would be excluded from the trial. Participants with side effects less severe than the above, but which they perceive as disruptive, will receive a further lozenge on a separate day before the start of the training intervention. Due to rapid tolerance to the adverse effects of nicotine, this pre-exposure will reduce unpleasant effects of nicotine during training. Furthermore, participants are asked not to chew the lozenge or swallow it whole. The lozenges dissolve over 10 min, thus enforcing a relatively slow rise in nicotine blood levels.

- Another risk is related to nicotine being an addictive substance. Nicotine addiction would be a serious but very unlikely risk. The likelihood of any reinforcing properties of the nicotine lozenge leading to abuse liability is very low. The abuse liability of a drug depends on the kinetics of drug delivery, such that reinforcing properties are greater for delivery routes associated with faster absorption. Nicotine plasma levels peak approximately 1 hour following administration of a nicotine polacrilex lozenge, and the protracted absorption of nicotine has been shown to not produce subjectively reinforcing effects. There is however a concern that nicotine lozenges may trigger relapse in former regular smokers because the subjective effects, even if not reinforcing in themselves, may be associated with dependent cigarette smoking and dependence-related effects of cigarette-derived nicotine. Thus, lozenge-derived nicotine may act as a priming cue. Risk minimization: Former smokers will not be included in this study.

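### The planned slope model is valid, but a common week-0 mean plus smoking terms would be a cheap precision gain: about 16% less variance at r=0.7 if week-0 means are equal and time is linear

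*Combined protocol and SAP*

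**What the plan says.** Sample Size and Data Analysis, item 1, gives the primary model for Hypothesis 1a as "OCM= time+ treatment+ treatment x time, with time as a continuous measure". The interaction is the treatment difference in slope. Week 14 enters only a secondary model with categorical time. No covariance structure is stated; the power formula uses a single within-subject correlation, r=0.7.

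Justification, Objective, & Research Design, item 2, sets the visits at "week 0 (day before training starts), weeks 4, 7 and 10 (after the training session"), plus a follow-up in week 14. It adds that "OCMs are assessed on a non-drug day (Wed").

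Study Procedures, item 1, places randomisation after screening and before the lozenge exposure session or sessions. The first outcome session comes after those. Exclusions can occur in between: "A participant who cannot tolerate the 2-mg lozenge even after repeated attempts will be excluded from the study". Blood pressure, heart rate and vomiting criteria also apply. On allocation, it says: "The number of smokers will be counterbalanced between the nicotine and placebo group". In the analysis, smoking status appears only as an exploratory factor.

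On numbers, the plan counts 20 completers per group, says "Although we will include subjects with partial data", and states that "we expect having to enroll 25 subjects per group into the training and having to screen approximately 70 subjects in total".

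**The concern.** The free treatment term lets the two arms start at different levels, so the slope difference is estimated from within-subject change alone. If the arms have the same expected score at week 0, that is information the model does not use. Constraining the week-0 mean to be common estimates the same contrast more precisely from the same data. Likewise, a factor balanced at allocation is usually kept in the primary model, and here it is absent.

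What is at stake is precision in a small proof-of-concept trial. Nothing here makes the planned test invalid.

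**Working it through.** **Inputs.** From the plan: visits at weeks 0, 4, 7 and 10; b=4; n=20 completers per group; r=0.7; Var(t)=0.185; z values 1.96 and 0.84. Assumed here: compound symmetry with SD 1 (the structure the plan's formula implies), and r=0.8 and 0.9 as alternatives. Time is t=weeks/10.

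**1. The plan's figure.** The exponents are garbled in the text and are read as a square and a square root.
d = sqrt[2(1.96+0.84)²(1-r)/(b n Var(t))] = sqrt[2 x 7.84 x 0.3/(4 x 20 x 0.185)] = 0.564. This reproduces the stated 0.56.

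**2. The planned model's actual variance.** The mean of t is 0.525 and Sxx = 0.5475. The generalised least squares (GLS) variance of the slope difference is 2(1-r)/(n Sxx) = 0.6/(20 x 0.5475) = 0.0548. The plan's formula implies 0.6/(4 x 20 x 0.185) = 0.0405. The two differ because 0.185 is the variance of four equally spaced times with divisor b-1, but it is multiplied by b. With divisor b the actual visits give 0.5475/4 = 0.137, and the same formula gives d = 0.66.

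**3. Common week-0 mean.** The fractional reduction in variance is A/[r + (1-r)/4 + A], where A = 0.525²(1-r)/0.5475.

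| r | A | Reduction | Variance, free | Variance, common mean |
|---|---|---|---|---|
| 0.7 (plan) | 0.1510 | 16.3% | 0.05479 | 0.04586 |
| 0.8 (assumed) | 0.1007 | 10.6% | 0.03653 | 0.03266 |
| 0.9 (assumed) | 0.0503 | 5.2% | 0.01826 | 0.01732 |

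At r=0.7:
- Detectable d at 80% power is 2.8 x sqrt(0.05479) = 0.66 for the planned model and 2.8 x sqrt(0.04586) = 0.60 for the common-mean model.
- Power at d=0.56 is Φ(0.56/0.2341 - 1.96) = 67% and Φ(0.56/0.2141 - 1.96) = 74%.
- The gain is worth 0.05479/0.04586 - 1 = 19% more patients.

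**4. Sensitivity of the reduction, r=0.7.**
- Partial data (assumed: 25 per group start, 5 stop after week 4 or after week 7): variances 0.05217/0.04427 or 0.04910/0.04118, a cut of 15% or 16%.
- Random slopes with variance 0.05 to 0.20, uncorrelated with the intercept: 14.9% down to 11.9%.
- The same slope variances with intercept-slope correlation +0.5: 6.8% down to 1.5%. With correlation -0.5: 26.2% up to 32.5%.

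**5. Cost if week-0 means differ.** The constrained slope is biased by [0.525(1-r)/0.5475]/[r + (1-r)/4 + A] x gap. At r=0.7 this is 0.2877/0.9260 = 0.31 x gap. With standard error 0.2141, Type I error is 5.2% at a gap of 0.1 SD, 6.0% at 0.2 SD and 11.2% at 0.5 SD. The constrained model keeps the lower mean squared error up to a gap of sqrt(0.05479-0.04586)/0.311 = 0.30 SD.

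**6. How large a gap is plausible.** If 70 consent, nobody fails screening and allocation is equal (assumptions), 35 per arm are randomised and 25 start training, so 10 of 35 are lost before training. If nicotine-arm losses are selective and placebo-arm losses are not, excluded participants who differ by 0.5 SD produce a gap of 0.14 SD (Type I error 5.5%). A difference of 1 SD produces 0.29 SD (7.0%).

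**7. Smoking.** Take half the sample as smokers and slopes differing by D = 0.1 to 0.3 SD over 10 weeks (assumptions). Smoking x time then removes D²/40 from the variance. That is 0.4% to 4% of the total in the planned model and 0.5% to 5% in the common-mean model.

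**The case against.** The strongest objection is that the design threatens the very assumption the gain needs. Week 0 comes after exposure to the allocated lozenge and after exclusions that are mainly reactions to nicotine, so losses may differ by arm. The planned model is unbiased under a constant week-0 gap; the constrained one is not. This stands, and it makes equality an assumption here. A direct lozenge effect on the week-0 score is unlikely, given testing on non-drug days and the stated "half-life: 2.3 hours for the lozenge" (Research Related Risks). Selection remains the main threat. The bound in step 6 is only a guide, because the 70 is approximate and an expectation, not a cap.

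Two further limits stand. First, a table of week-0 means cannot settle the matter: with 20 per arm the standard error of the difference is sqrt(2/20) = 0.32 SD, and a true 0.30 SD gap would be detected only about 16% of the time. Second, the two models estimate the same contrast only if time is linear. With equal week-0 means and illustrative nicotine advantages of 0, 0.5, 0.3 and 0.1 SD, the free model gives a slope difference of 0.07 and the constrained model 0.13. Disagreement between them would therefore not by itself show a baseline gap.

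A reader might infer that the plan ignores baseline, or that its primary test is biased. The documents support neither: week 0 is one of the four responses, and the interaction is a proper slope contrast. Nor do they support the opposite inference, that randomisation alone guarantees equal week-0 means among those who start training.

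**Conclusion.** This is an optional, low-cost improvement to a valid analysis. Under equal week-0 means, linear time, compound symmetry and the plan's r=0.7, a common week-0 mean reduces the variance of treatment x time by about 16%. The reduction is 11% and 5% at the assumed r of 0.8 and 0.9. It is 12% to 15% at r=0.7 with uncorrelated random slopes, and about 1.5% to 33% if intercepts and slopes correlate between +0.5 and -0.5. Because the plan states no covariance structure, the figure cannot be narrowed further.

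The gain should not be read as moving power from 80% to something higher at d=0.56. For the actual visit times the planned model has about 67% power there, and the common-mean model about 74%. The planned model does not match its own power formula numerically, although the percentage reductions do not depend on that.

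The change remains reasonable because the gap needed to lose the mean-squared-error advantage is about 0.30 SD and the planned model is still reported. The smoking terms are justified by the allocation; their gain in precision is small and rests on assumed slope differences.

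**What to change.** Before unblinding, pre-specify as primary: OCM = time + treatment x time + smoking + smoking x time, with time zero at week 0 and no treatment main effect. State the covariance structure. Name the planned free-intercept model as the sensitivity analysis and report it beside the primary. Tabulate by arm the week-0 means and the participants excluded between randomisation and week 0. Say in advance that a difference between the two models may reflect either a week-0 gap or non-linear time. Keep smoking x treatment x time exploratory.

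If the sponsor will not rest the primary test on equal week-0 means, the two models can swap roles; either choice must be fixed before unblinding.

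The cost is a few lines of model wording and one table, with no new data. The price is reliance on an assumption that the planned model does not need.
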